Power calculations were carried out by the VUmc Department of Epidemiology and Biostatistics. Based on previous RCTs on PM+ (Bryant et al., 2017; Rahman et al., 2016), we aim for a conservatively estimated small to medium Cohen's *d* effect size of 0.4 in the PM+ group at 3-months follow-up. Power calculations suggest a minimum sample size of 133

participants per group (power = 0.90, α = 0.05, two-sided). Taking into account an expected 30% attrition rate at the 3-month follow-up, we aim to include a total number of 380 participants (190 in the CAU/PM+ group and 190 in the CAU group).

Randomization

After baseline, participants will be randomized into the CAU/PM+ group or CAU group. Permuted blocks randomization will be performed using computerized software on a 1:1 basis and by means of sealed opaque envelopes. Household members will be randomized together to decrease the risk of contamination. The first PM+ session will be scheduled within one week after the baseline assessment.

Problem Management Plus (PM+)

We will test individual PM+ delivered by Syrian peer-refugees. During this 5-week intervention, a new treatment strategy is introduced in every session and subsequently reviewed in all following sessions. Stress management is practiced in session 1 using a slow breathing exercise. Problem management is taught in session 2 using a step-by-step plan to pro-actively manage practical problems. Behavioral activation is introduced in session 3 by encouraging the participant to re-engage with pleasant and task-oriented activities. Strategies to strengthen social support are discussed in session 4. Homework assignments are carried out between the sessions and relapse prevention strategies are discussed in session five (Dawson et al., 2015; Sijbrandij et al., 2017).

The adaptation of the PM+ intervention and development of training materials was coordinated by the Danish Red Cross in collaboration with the WHO and partners in STRENGTHS. Adaptations were made according to a framework for the cultural adaptation of psychological interventions (Bernal & Sáez-Santiago, 2006), and involved a literal

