sessions for protocol adherence purposes. A random sample of 10% of the audio recordings will be coded by an independent researcher with in-depth knowledge of PM+. Helpers will complete fidelity checklists addressing the PM+ components during the sessions (cf. Bryant et al., 2017; Rahman et al., 2016).

Trial monitoring and adverse events reporting

The VU research team has full access to the trial dataset. Adverse events (AE) or serious adverse events (SAE) are defined as any undesirable experience occurring to a participant during the study, whether or not considered related to the trial procedure or the PM+ intervention. All SAEs will be recorded in Castor EDC trial monitoring software (Ciwit BV, 2018) and reported to the SB and to the Central Committee on Research Involving Human Subjects within 7 days (in case of death or life-threatening situation) or 15 days (all other SAEs) after being informed about the event. SAEs will be followed-up until they have abated or until a stable situation has been reached, and if necessary, referral to a general physician will be made.

Analysis

To measure comparisons at baseline between the two treatment groups, t-test (continuous variables) or chi-square tests (categorical variables) will be conducted for normally distributed data; Mann-Whitney tests will be conducted for continuous non-normally distributed data.

Both intention-to-treat (ITT) analysis, including all randomized participants ($N=380$), and completers' analysis will be carried out. The main conclusion will be based on the ITT analysis. To estimate the treatment effect, a linear mixed model will be employed for the primary endpoint analysis, which will have treatment as fixed effects, baseline measurement of primary endpoint as covariate, and subject as random effects. The mean difference between

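### Household members are randomised together, but the mixed models have no household term and the power calculation assumes independent participants

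*Protocol*

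**What the plan says.** Three parts of the protocol's Methods bear on this point.

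- **Randomization.** Allocation is individual and balanced: "Permuted blocks randomization will be performed using computerized software on a 1:1 basis". One rule is added: "Household members will be randomized together to decrease the risk of contamination". A household with two or more participants is therefore allocated as a unit.
- **Analysis.** The linear mixed model for the primary endpoint has treatment as fixed effect, with "baseline measurement of primary endpoint as covariate, and subject as random effects". The secondary outcomes get the same structure. The difference between arms and its 95% confidence interval come from this model. Hierarchical linear modelling is mentioned, but subject is the only grouping level named.
- **Sample size.** The target is a Cohen's d of 0.4 three months on, with 90% power and a two-sided alpha of 0.05. The result for each arm is given as: "Power calculations suggest a minimum sample size of 133". The only inflation is for dropout: "Taking into account an expected 30% attrition rate at the 3-month follow-up". This leads to 190 per arm, or 380 in all.

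The protocol gives no intraclass correlation (ICC), no expected household size and no design effect. It does not limit enrolment to one participant per household.

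**The concern.** The analysis should respect the way participants were allocated. A subject random effect captures correlation between repeated measurements on one person. It does not capture correlation between two people who live together and were allocated together. If that correlation is positive, two such participants carry less information about the treatment difference than two unrelated ones, and a model that treats them as independent understates the standard error.

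Two things are at stake. The first is validity: intervals too narrow and type I error above 5% for both HSCL-25 primary outcomes, and for any secondary outcome that is correlated within households. The second is the stated power of 0.90, which contains no allowance for shared households. Validity is the weightier of the two, because a gain in precision elsewhere does not restore it.

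**Working it through.** **Inputs from the protocol:** d = 0.4 (so SD = 1), power 0.90, two-sided alpha 0.05, 133 evaluable per group, 30% attrition, 190 per group.

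**Inputs not in the protocol (assumptions):** the share *f* of analysed participants who belong to a pair from one household, and the within-household ICC.

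**Step 1. Reproduce the plan's figure.** A two-sample t-test with d = 0.4 needs 132.3 per group for 90% power. With 132 per group the power is 0.899; with 133 it is 0.901. Then 133 / 0.70 = 190.0 per group, and 2 × 190 = 380. The arithmetic is correct. It is that of independent participants, and no allowance for clustering is hidden in the rounding.

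**Step 2. Design effect.** With DE = 1 + (m* − 1) × ICC and m* = Σm² / Σm, a share *f* in pairs and the rest alone gives m* = 1 + *f*, so DE = 1 + *f* × ICC.

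**Step 3. Consequences.**

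- Factor by which the interval should be wider: √DE.
- Actual type I error of the unadjusted-for-clustering test: 2 × [1 − Φ(1.96 / √DE)].
- Power at 133 per group, without baseline adjustment: noncentral t with the variance multiplied by DE.

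| Share in pairs | ICC | DE | Interval should be wider by | Type I error | Power |
|---|---|---|---|---|---|
| 10% | 0.1 | 1.01 | 0.5% | 5.1% | 0.899 |
| 20% | 0.2 | 1.04 | 2.0% | 5.5% | 0.890 |
| 30% | 0.3 | 1.09 | 4.4% | 6.0% | 0.876 |
| 50% | 0.3 | 1.15 | 7.2% | 6.8% | 0.858 |
| 60% | 0.5 | 1.30 | 14.0% | 8.6% | 0.813 |

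Worked line: *f* = 0.5 and ICC = 0.3 give DE = 1 + 0.5 × 0.3 = 1.15 and √1.15 = 1.072. Then 1.96 / 1.072 = 1.828, and 2 × [1 − Φ(1.828)] = 0.068.

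The second to fourth lines are the range treated here as plausible. The first shows that the effect can be negligible. The last needs both a high share and a high ICC.

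**Step 4. Attrition.** The share that counts is the share among analysed participants. If 30% drop out independently within pairs (an assumption; correlated dropout lessens the effect), only 70% of retained pair members still have their partner in the analysis. The last line, read as 60% of enrolled participants, becomes DE = 1 + 0.6 × 0.7 × 0.5 = 1.21, with type I error 7.5% and power 0.84. For 30% enrolled in pairs and ICC 0.3, DE = 1 + 0.3 × 0.7 × 0.3 = 1.06, with type I error 5.7% and power 0.88.

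**Step 5. Baseline adjustment.** The planned model adjusts for baseline; the 133 does not use this. With baseline-outcome correlation ρ, the residual variance is multiplied by (1 − ρ²). Holding DE at 1.15, the power at 133 per group is 0.89 for an assumed ρ = 0.3 and 0.94 for ρ = 0.5. At DE 1.30 and ρ = 0.5 it is 0.91. Adjustment can thus bring power back to 0.90 or above, but at a given DE the type I error in step 3 is unchanged.

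**The case against.** The strongest reply is that this is an individually randomised trial with a few incidental small clusters. Each member of a household must separately consent, exceed both screening cut-offs and not be in specialised psychological treatment, which limits co-enrolment. The protocol gives neither the share of shared households nor an ICC, so the size of any error is unknown. The ICC that matters is the one conditional on baseline; where household members resemble each other mainly in stable symptom level, adjustment lowers it. The statistical analysis plan is not shown and may add a household term.

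Much of this stands. It limits the size of the problem and rules out presenting the magnitude as known. A reader might infer that the trial is underpowered or needs more participants. The documents do not support that: the shares and ICCs are assumptions, attrition breaks up some pairs, and baseline adjustment may return power to 0.90 or more. A reader might also take narrow intervals as established for every outcome. That too goes beyond the protocol, which reports no within-household correlation for any of them.

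The mismatch itself remains. The protocol is not silent on the random effects: it names them, and household is not among them. It foresees shared households, since it makes a rule for them. Baseline adjustment cannot remove correlation that arises after baseline, such as from a shared asylum decision or from receiving the intervention in the same household. The degrees-of-freedom method and the resampling unit of the economic bootstrap are commonly left to the statistical analysis plan, and their absence is no fault here.

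**Conclusion.** The point holds as a mismatch between the stated randomisation and the stated analysis. That part is certain from the text. The direction of the error rests on two conditions: some households contribute two or more analysed participants, and their outcomes are positively correlated given baseline. Both are likely; neither is quantified in the protocol.

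The size is probably modest. Over the range treated as plausible (20-50% of analysed participants in pairs, ICC 0.2-0.3), intervals should be about 2-7% wider, with the type I error and unadjusted power shown in the middle lines of the table. The loss of power is the weaker half of the point, because baseline adjustment may offset it; the standard errors are the firmer half. This is something that should be fixed. It does not call the randomisation, the endpoints or N=380 into question.

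**What to change.** 1. Record a household identifier for every participant; the trial already needs this information to allocate household members together.
2. In the Analysis section, add a household random intercept to the primary and secondary mixed models, with subject nested in household and single participants as clusters of one. Alternatively, use household-clustered standard errors, and name them as the fallback, for example if the household variance is estimated at zero, which can happen when most households have one participant. Fix this choice before unblinding.
3. In the Sample size section, say that 0.90 assumes independent participants, and give the power under a stated household design effect with its assumed share and ICC. Keep N=380.

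The cost is one data field and a few sentences. Intervals become slightly wider and the stated power slightly lower. No additional participants are needed. If shared households turn out to be rare, the results will hardly change.

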translation by an Arabic-speaking translator, qualitative interviews with stakeholders such as Syrian refugees and mental health professionals (cf. Applied Mental Health Research Group, 2013), and cognitive testing of the literally translated manual. The core components of the PM+ intervention (e.g., breathing exercise) were retained, while case examples were rephrased to fit the context of Syrian refugees.

PM+ will be delivered by Arabic-speaking male and female refugees from Syria who have completed high school, have a background in education, social work, health care or another related field, and with sufficient speaking ability in Dutch or English. They will receive eight days of training, followed by two practice cases, and close supervision by trained PM+ trainers and supervisors throughout the trial. The training of helpers (ToH) involves education about common mental disorders, basic counselling skills, delivery of intervention strategies and self-care (Rahman et al., 2016).

PM+ trainers and supervisors will be licensed mental health care professionals. They will be trained in a five-day training-of-trainers (ToT) program. The ToT covers the elements of the ToH as well as training and supervision skills (Rahman et al., 2016). Face-to-face supervision of helpers will take place on a weekly basis. The supervisors themselves will be supervised fortnightly by the master trainer who provided the ToT. This training model has previously been successfully implemented (Dawson et al., 2015).

Care as usual

Care as usual (CAU) includes all (mental) health services available to refugees in the Netherlands. Health care for asylum seekers is organized and financed on a national level by the Central Agency for the Reception of Asylum Seekers (COA). Health care, including mental health care for adults is provided by a COA-contracted insurer, and public health care is provided by Community Health Services, Regional Medical Emergency Preparedness and

Planning (GGD-GHOR) and the Centre for Youth and Family (CJZ). Resettled Syrian refugees with a residence permit have to pay a basic health insurance, and have access to health services through their local general practitioner (Fuhr et al., In Press; Kroneman et al., 2016).

Screening measures

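### The stated models allow for no clustering by peer helper in the PM+ arm, so if outcomes differ between helpers the standard error is too small for inference beyond those helpers

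*Protocol*

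**What the plan says.** Under Problem Management Plus (PM+), the protocol says "We will test individual PM+ delivered by Syrian peer-refugees" and that "PM+ will be delivered by Arabic-speaking male and female refugees from Syria". The Background describes five weekly 90-minute sessions with a non-specialist helper. Under Care as usual, the comparator is the health services already available to refugees, with no PM+ helper.

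Under Analysis, the primary model is a linear mixed model with treatment as fixed effect, "baseline measurement of primary endpoint as covariate, and subject as random effects". The secondary outcomes get the same structure. The covariate-adjusted version adds baseline covariates only. Hierarchical linear modelling is mentioned where the software is named, but no further level is defined.

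Under Sample size, the target is an "effect size of 0.4 in the PM+ group at 3-months follow-up". The text continues "Power calculations suggest a minimum sample size of 133" "participants per group (power = 0.90, α = 0.05, two-sided", allows for 30% attrition and arrives at "190 in the CAU/PM+ group and 190 in the CAU group". No design effect, helper number, caseload or ICC is given.

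**The concern.** The design is partially nested: PM+ participants may share a helper, CAU participants do not. A subject random effect handles repeated measurements on one person. It cannot represent correlation between different people treated by the same helper. Some variation between helpers is plausible on the protocol's own description, since they are non-specialists who start after eight days of training and two practice cases.

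At stake is what the confidence interval describes. Without a helper term it describes the effect as delivered by these particular helpers. The abstract and Discussion look towards scaling up through the WHO, which means delivery by other people. For that purpose an interval that leaves out between-helper variation is too narrow, for the primary and all secondary outcomes alike. Because the protocol specifies the random effects, an analysis plan that followed this text would carry the omission forward.

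**Working it through.** **Inputs from the protocol (Sample size):** d = 0.4 (SD = 1 on the standardised scale), power 0.90, two-sided α = 0.05, 133 per group, 30% attrition, 190 per arm.

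**Assumed, because the protocol does not state them:** k = 10 to 20 helpers, ICC = 0.02 to 0.10, equal caseloads, 133 analysed per arm, no gain from the baseline covariate.

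**Step 1: reproduce the plan's figure.** The normal approximation gives n = 2 × (1.960 + 1.282)² / 0.4² = 131.3, so 132 per arm. The two-sample t-test version gives 132.3, so 133. Then 133 / 0.70 = 190 per arm and 380 in total. The stated figures therefore follow from independent observations, that is, a design effect of 1.

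**Step 2: variance with helper clustering in one arm.** The caseload is m = 133 / k. The PM+ design effect is DE = 1 + (m − 1) × ICC. The variance inflation of the arm difference is VI = (1 + DE) / 2, and the standard error grows by √VI.

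**Step 3: consequences.**
- Type I error of the planned test, with a zero average effect and helpers that differ: 2 × [1 − Φ(1.96 / √VI)].
- Power of an analysis that uses the correct standard error: noncentral t with noncentrality 0.4 / √(2 × VI / 133) and 264 degrees of freedom. At VI = 1 this is 0.901.
- Rejection rate of the planned test at d = 0.4: the chance that the estimate exceeds 1.96 uncorrected standard errors in either direction, given the larger true standard error (normal approximation).

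| Helpers | ICC | m | DE | VI | SE ratio | Type I error, planned test | Power, correct analysis | Rejection rate at d = 0.4, planned test |
|---|---|---|---|---|---|---|---|---|
| 20 | 0.02 | 6.65 | 1.113 | 1.06 | 1.028 | 5.7% | 0.885 | 0.897 |
| 15 | 0.05 | 8.87 | 1.393 | 1.20 | 1.094 | 7.3% | 0.844 | 0.883 |
| 10 | 0.10 | 13.3 | 2.230 | 1.62 | 1.271 | 12.3% | 0.725 | 0.847 |

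Worked line for 15 helpers and ICC 0.05: DE = 1 + 7.87 × 0.05 = 1.393; VI = 2.393 / 2 = 1.197; √VI = 1.094; 1.96 / 1.094 = 1.792; two-sided tail = 7.3%.

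**Step 4: the mild end.** With 30 helpers and ICC 0.02, DE = 1.069, VI = 1.034, the standard error is 1.7% larger and type I error is 5.4%. With 20 or more helpers and ICC at most 0.02, the standard error rises by no more than about 3%.

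The power figures use 264 degrees of freedom. With few helpers the effective number would be lower, and power somewhat lower still.

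**The case against.** The strongest reply is that nothing in the protocol shows a positive helper ICC, and several features argue for a small one. Helpers need a relevant background, follow a manual and have weekly face-to-face supervision. They complete fidelity checklists, and 10% of recordings are coded. The host institution works country-wide, so the helper pool may be large. This stands as a limit on size. It does not show that the ICC is zero.

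A second reply concerns the null hypothesis. Allocation is by person or household, not by helper. If PM+ changes nothing for anyone, helpers cannot create correlation through treatment, and the planned test is not inflated on that account. The inflated rates apply only where some helpers do better than CAU and others worse, averaging to zero. That is correct, and the figures above are labelled accordingly.

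A third reply is that inference restricted to the trial's own helpers is legitimate, and that scaling up is presented as a later step after a positive evaluation. This also stands in part. It makes the point one about the population to which the interval applies.

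Finally, provider effects are often left to an analysis plan. Here, however, the protocol itself names the random effects for both primary and secondary outcomes.

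**Conclusion.** The point holds conditionally. The protocol sets out a subject-only random-effects structure and an independence-based sample size for a design in which only one arm can be clustered by helper. If the helper ICC is above 0 and helpers treat more than one participant, the standard error is too small for inference beyond these helpers. Under the assumed 10 to 20 helpers and ICC of 0.02 to 0.10, it should be about 3% to 27% larger. The actual size cannot be determined from the protocol and may be negligible.

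A reader might infer four stronger things that the document does not support:
- That type I error is above 5% outright. This needs a positive ICC and the particular null described above.
- That the planned test's power falls to about 0.72. That figure belongs to the corrected analysis; the planned test would reject at about 0.90 to 0.85, but with an error rate that is not controlled.
- That the helper pool is small and each helper treats many people. The protocol gives no numbers, although shared helpers are very likely with 190 participants and five sessions each.
- That helper identity is not recorded. The protocol does not say so, and helpers complete session checklists.

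Households randomised together are a separate source of clustering and are not part of this point.

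**What to change.** Amend the Analysis text to a partially nested mixed model for the primary and secondary outcomes: a helper random effect that applies in the PM+ arm only, CAU participants treated as singletons, and small-sample degrees of freedom. Ensure that the helper identifier is in the analysis dataset, and report the estimated helper ICC with the results. In the Sample size section, state that the 90% power assumes no helper clustering.

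The cost is a wording change and one variable. Recruitment, treatment and assessments are unaffected. The intervals will be slightly wider, and a fallback must be stated in advance in case the helper variance does not converge, which is more likely if helpers are few.

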After IC is obtained, participants will be asked to complete the two self-report measures on psychological distress (K10) and daily functioning (WHODAS 2.0). Participants who meet the inclusion criteria will be assessed for suicidal ideation (PM+ manual suicidal thoughts interview) and severe disorders (PM+ manual observation checklist). The independent assessors will refer individuals meeting any of the exclusion criteria to specialist support according to their needs.

Participants who meet all inclusion criteria will complete the baseline assessment at the same visit. This involves questionnaires on depression and anxiety (25-item Hopkins Symptoms Checklist; HSCL-25), trauma exposure (Trauma Experiences checklist), daily

stressors (Post-Migration Living Difficulties; PMLD), posttraumatic stress (PTSD Checklist for DSM-5; PCL-5), self-identified problems (Psychological Outcomes Profiles; PSYCHLOPS), anger (Trait Anger Scale; STAS-T), and questions on access to health services. Furthermore, the assessor will administer a health service utilisation and productivity impact interview (locally adapted version of the Client Service Receipt Inventory; CSRI).

The post-assessment (WHODAS 2.0, HSCL-25, PMLD, PCL-5, PSYCHLOPS, CSRI) is scheduled 6 weeks after the baseline assessment (or 1 week after the 5th PM+ session). The follow-up assessments are scheduled 3 months after the 5th PM+ session (WHODAS 2.0, HSCL-25, PMLD, PCL-5, PSYCHLOPS, STAS-T, CSRI) and 12 months after baseline (all 3-month follow-up measures and the Traumatic Experiences checklist, except the STAS-T). We also measure hair cortisol concentrations (HCC) at baseline and 3-month follow-up to investigate the effect of PM+ on HCC.

All questionnaires, except the exclusion instruments (the PM+ manual's suicidal thoughts interview and assessment tool for severe disorders) and the CSRI interview are self-administered on a tablet with audio functions (cf. Morina et al., 2017). Independent Arabic-speaking assessors with at least a degree-level will carry out the assessments. Assessors will receive a three-day training on the administration of questionnaires, use of the tablets, general interview techniques, common mental disorders, psychological first aid and ethical research conduct. The assessors are blinded to treatment allocation.

Sample size

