An overview of all study measures is provided in Table 1. The WHODAS 2.0 is a generic instrument to assess health and disability and is used across all diseases, including mental, neurological and substance use disorders. It is easy to administer, applicable across cultures and can be used in all adult populations. The cross-culturally validated 12-item version covers difficulties that people experience due to their illness across six domains during the last 30 days (WHO, 2010). Difficulties are scored on a five-point Likert scale ranging from 1 (none) to 5 (extreme), before summation (range 12-60). In line with the earlier RCTs on PM+ a cut-off of >16 will be used (Bryant et al., 2017; Rahman et al., 2016). The WHODAS will also be administered as secondary outcome measure.

The K10 will be used to measure psychological distress. Ten items related to depression and anxiety are rated on a five-point Likert scale, before summation (range 10-50). The K10 has been validated in Arabic-speaking populations (Fassaert et al., 2009; Sulaiman-Hill & Thompson, 2010). In a study among Kurdish and Afghan (former) refugees and asylum seekers in New Zealand and Australia the following cut-off scores were used: 10-15.9 (low risk of psychological distress), 16-21.9 (moderate levels of distress consistent with a diagnosis of moderate depression and/or anxiety disorder), 22-29.9 (high level of distress) and 30 or more (possibility of very high or severe levels of distress) (Sulaiman-Hill & Thompson, 2010). In the current study, we will use a score of >15 as an indication of moderate to high levels of psychological distress.

Sociodemographic information (sex, age, education, work, marital status and time elapsed since displacement) will be collected through items based on the demographic section of the WHODAS 2.0.

[Insert Table 1 here]

Primary outcomes

The primary outcomes are the level of depression and anxiety 3 months after the post-assessment (or fifth PM+ session), as measured by the HSCL-25. The HSCL-25 is a self-report questionnaire for symptoms of psychological distress (Derogatis, Lipman, Rickels, Uhlenhuth, & Covi, 1974). Items are rated on a four-point (1-4) Likert scale. Item mean scores can be calculated for the depression (15 items) and anxiety subscales (10 items). The HSCL-25 has been used with Syrian refugees (e.g., Acarturk et al., 2016).

Secondary outcomes

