the two arms at each assessment with its 95% confidence interval will be derived from the mixed model. The effects of PM+ on secondary outcomes (i.e., functional impairment, symptoms of PTSD, self-identified problems, anger, health and productivity costs, and HCC) will be examined using linear mixed models with treatment as fixed effects, baseline measurement as covariate, and subject as random effects. Covariate-adjusted mixed model of primary endpoint will also be performed by adding relevant covariates at baseline (e.g., gender, age, education, baseline levels of depression, anxiety, PTSD, traumatic experiences, post-migration living difficulties, and HCC hypo- versus hypersecretion, etc.) to the above-mentioned model.

For the economic analysis incremental cost-effectiveness ratios (ICERs) will be generated comparing changes in mean costs and primary outcomes from a payer and societal perspective between the two arms. Non-parametric bootstrapping analyses to derive 95% confidence intervals around ICERs , and cost-effectiveness acceptability curves will be generated showing the likelihood that PM+ would be cost-effective at different willingness-to-pay thresholds.

Descriptive analyses will be carried out in SPSS and hierarchical linear modeling analyses in R version 3.6.0. Across all analyses, two-tailed tests will be reported with $p < 0.05$.

Interview transcripts from the process evaluation will be analyzed thematically following the framework approach (Pope, Ziebland, Mays, & Mays, 2000) using NVivo version 11 (QSR International Pty Ltd, 2015).

Discussion

In this RCT we aim to evaluate the effectiveness and cost-effectiveness of the peer-refugee delivered PM+ intervention among Syrian refugees in the Netherlands impaired by symptoms

of psychological distress. Within the larger STRENGTHS project, other RCTs with different modes of delivery (see Sijbrandij et al., 2017) will be conducted among Syrian refugees in Europe and the Middle East, which will strengthen external validity of trial findings and provide a potential model for scaling up in both high- and low-income settings.

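### The mixed model as listed has no visit or treatment-by-visit term, so it cannot yield the 3-month effect or the per-assessment differences that the protocol promises from it

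*Protocol*

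**What the plan says.** The model terms are given once for the primary endpoint in the Analysis section: "which will have treatment as fixed effects, baseline measurement of primary endpoint as covariate, and subject as random effects". The following sentence says that the mean difference between "the two arms at each assessment with its 95% confidence interval will be derived from the mixed model". For the secondary outcomes the same section repeats the structure, "linear mixed models with treatment as fixed effects, baseline measurement as covariate, and subject as random effects". The covariate-adjusted version adds only baseline variables.

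The Primary outcomes section fixes the time point: "The primary outcomes are the level of depression and anxiety 3 months after the post-assessment" (or the fifth session), measured with the HSCL-25, which has separate depression and anxiety subscales. The Sample size section sets d = 0.4 at the 3-month follow-up.

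The Procedure section puts HSCL-25 at three follow-ups. The first is early: "The post-assessment (WHODAS 2.0, HSCL-25, PMLD, PCL-5, PSYCHLOPS, CSRI) is scheduled 6 weeks after the baseline assessment". The others are 3 months after the fifth session and 12 months after baseline. Anger and hair cortisol (HCC) are each scheduled at baseline and at the 3-month follow-up only.

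**The concern.** The listed fixed part contains treatment and baseline. Fitted to three follow-ups per participant, it has one treatment coefficient and therefore the same arm difference at every visit. Two stated aims cannot be met with those terms: a difference at each assessment, and an estimate of the effect at the 3-month primary time point.

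The protocol rests its main conclusion on the intention-to-treat analysis, for which this is the stated primary model. If the terms were applied literally, an early effect that had gone by 3 months could still produce a significant coefficient, and a late effect would be diluted. If they were not, the analyst would have to choose between a pooled and a 3-month result without a written rule.

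**Working it through.** **The plan's own figure.** Two-sample comparison, d = 0.4, two-sided α = 0.05, power 0.90: n = 2(1.960 + 1.282)²/0.4² = 131.3, so 132 per group by the normal formula. The t-test version gives 132.31, rounded up to 133. Allowing for 30% attrition, 133/0.70 = 190 per group and 380 in total. The stated figures are reproduced, and they are figures for a 3-month contrast.

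**What the listed model estimates.** From the protocol: 190 per arm, and 70% retention at 3 months. Assumed: SD 1, equal correlation 0.6 between all measurements including baseline, monotone retention of 80% at post-assessment and 60% at 12 months, equal in both arms.

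1. Given baseline, each follow-up has variance 1 − 0.6² = 0.64 and each pair has covariance 0.6 − 0.6² = 0.24. The random-intercept variance is thus 0.24 and the residual variance 0.40.
2. A participant with m visits contributes weight 1/(0.40 + 0.24m) per visit: 1/0.64 = 1.5625 for m = 1, 1/0.88 = 1.1364 for m = 2, 1/1.12 = 0.8929 for m = 3.
3. The retention pattern means 60% have three visits, 10% have two and 10% have one. Weight by visit:
   - Post-assessment: 0.6(0.8929) + 0.1(1.1364) + 0.1(1.5625) = 0.806
   - 3 months: 0.6(0.8929) + 0.1(1.1364) = 0.649
   - 12 months: 0.6(0.8929) = 0.536
4. The total is 1.991, so the shares are 0.405, 0.326 and 0.269. The 3-month visit supplies about a third of the estimate, and earlier visits weigh more because fewer data are missing.

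Applying these shares to assumed true effects (SD units):

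| Post / 3 months / 12 months | Pooled coefficient | True 3-month effect |
|---|---|---|
| 0.4 / 0.4 / 0.4 | 0.40 | 0.40 |
| 0.5 / 0.4 / 0.2 | 0.39 | 0.40 |
| 0.6 / 0.4 / 0.2 | 0.43 | 0.40 |
| 0.5 / 0.4 / 0 | 0.33 | 0.40 |
| 0 / 0.4 / 0.4 | 0.24 | 0.40 |
| 0.6 / 0 / 0 | 0.24 | 0 |

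**Rejection in the last row.** Standard error = 1/√(380 × 0.25 × 1.991) = 0.073. Then 0.243/0.073 = 3.34, and the probability of exceeding 1.96 is about 0.92. Simulation under the same assumptions gives 90% to 92%, while a 3-month contrast rejects in 4.5%.

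**Does adding the terms cure it?** In large simulated data (8,000 participants, correlation 0.5, full follow-up) with true effects 0.6/0.4/0.2, the model with visit and treatment-by-visit returned 0.59/0.42/0.16. The listed model returned the single value 0.39. A visit main effect alone would still leave one treatment coefficient.

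**The case against.** The strongest reply is that the term list is shorthand. The promise of a difference at each assessment, the 3-month endpoint and the 3-month power calculation all point to a visit-specific contrast, and a statistical analysis plan not shown here may spell it out. The same sentence is applied to anger and HCC, where a subject random effect cannot be separated from residual error, which also suggests a template. This stands as a reading of intent. It does not remove the contradiction, because the protocol lists the terms and then promises results that those terms cannot give.

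Nor can the model be rescued by supposing that it uses 3-month data alone. The random subject effect would then be unidentifiable, and the reference to each assessment would have no meaning. That all three visits enter one model is still an inference, though the only one that fits the wording.

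Several stronger readings are tempting but not supported:

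- A reader might infer that the trial will test the pooled coefficient and report it as the 3-month effect. The protocol never names the pooled coefficient as the primary test.
- A reader might infer a large bias in general. Gradual fading gives 0.39 or 0.43 against 0.40; the large discrepancies need late onset or complete loss of effect, and the 90% figure comes from a deliberately extreme profile.
- A reader might infer that costs would be pooled over recall periods of very different length. The protocol states no recall period for the service-use interview, and cost-effectiveness has its own bootstrap analysis.
- A reader might infer that time trends would leak into the treatment effect through different attendance by arm. The protocol gives no arm-specific attendance, and the calculations above assume equal retention.
- A reader might extend the averaging problem to every secondary outcome. It does not reach anger or HCC.

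**Conclusion.** The point holds as an internal contradiction in the stated analysis, most likely an incomplete specification. The listed terms give one data-weighted average over post-assessment, 3 months and 12 months. With a true 3-month effect of 0.40 SD, that average ranged from 0.24 to 0.43 across the profiles shown, and it is correct under a constant effect. The visit effects, the correlation of 0.6 and the 80% and 60% retention are assumptions; only the 30% attrition at 3 months is in the protocol. The contradiction itself depends on none of them. Because this is the primary model, it should be corrected before analysis. The sample size stands.

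**What to change.** For outcomes measured at more than one follow-up, state the fixed effects as treatment, categorical visit, treatment-by-visit and baseline, with subject as a random effect. Name the treatment contrast at 3 months as the primary test for each of the two HSCL-25 primary outcomes, depression and anxiety, and make the post-assessment and 12-month contrasts secondary. Carry the same visit terms into the covariate-adjusted model. For anger and HCC, use a baseline-adjusted regression without a subject random effect. Baseline-by-visit terms and an unstructured covariance are optional.

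This takes a sentence or two and no new data. The cost is precision. Under the assumptions above, the pooled coefficient has a standard error of 0.073, whereas a 3-month comparison using 3-month data alone has √(0.64/(380 × 0.25 × 0.70)) = 0.098; the repeated-measures contrast should be at or slightly below that. The 3-month contrast is the quantity for which 133 per group and 380 in total were calculated, so neither figure changes.
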